During the Phase 1 Study ESKETINTRD1002, 15 healthy Japanese and 14 healthy Caucasian subjects received single intranasal doses of esketamine 28 mg, 56 mg, and 84 mg in a crossover manner.¹³ The mean body mass index (BMI) were 21.98 kg/m² and 23.49 kg/m² in Japanese and Caucasian subjects, respectively. On average, plasma esketamine C_{max} and AUC values were up to 48% higher in Japanese subjects compared with Caucasian subjects. The incidence of the treatment-emergent adverse events (TEAEs) was higher in Japanese subjects (80% [12/15]) as compared to Caucasian subjects (50% [7/14]). The most commonly reported TEAEs by preferred term (>10%) in Japanese subjects were headache (26.7% [4/15] of subjects), vertigo (46.7% [7/15] of subjects), vomiting (26.7% [4/15] of subjects), derealization (20.0% [3/15] of subjects), nausea (20.0% [3/15] of subjects), depressed level of consciousness (13.3% [2/15] of subjects), somnolence (13.3% [2/15] of subjects), and confusional state (13.3% [2/15] of subjects). Though TEAEs were seen in majority of subjects, they were transient, mild or moderate in severity and were consistent with previously reported TEAEs for esketamine. Hence, a single intranasal dose of esketamine (28 mg, 56 mg, and 84 mg) was observed to be safe and well tolerated in Japanese subjects with no new safety findings of clinical concern.

Study ESKETINTRD1003 compared the PK, safety, and tolerability of intranasally administered esketamine in healthy elderly (≥ 65 years of age) and younger adult subjects (18 to 55 years of age, both inclusive).¹⁴ Subjects received a single intranasal treatment of esketamine 28 mg. Median time to reach the maximum plasma concentration (t_{max}) of esketamine was approximately 30 minutes for both age groups. The geometric means of the C_{max} and area under the plasma concentration-time curve from time 0 to infinite time, AUC_{∞} , for esketamine were approximately 21% and 17% higher, respectively, in the elderly compared with younger adult subjects.¹⁴

Another Study, ESKETINTRD1012, compared the PK, safety, and tolerability of intranasally administered esketamine in elderly subjects (≥ 75 years of age) and healthy younger adult

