- Suggestive of abuse potential (Aggression, Confusional state, Decreased activity, Dependence, Disorientation, Dissociation, Dissociative disorder, Dizziness, Drug abuse, Drug abuser, Drug dependence, Drug use disorder, Drug detoxification, Drug diversion, Drug rehabilitation, Drug tolerance, Drug tolerance increased, Drug withdrawal convulsions, Drug withdrawal headache, Drug withdrawal syndrome, Euphoric mood, Feeling abnormal, Feeling drunk, Feeling of relaxation, Hallucination, Hallucination, auditory, Hallucination, gustatory, Hallucination, olfactory, Hallucination, synaesthetic, Hallucination, tactile, Hallucination, visual, Hallucinations, mixed, Inappropriate affect, Mental impairment, Product tampering, Psychomotor hyperactivity, Psychotic disorder, Rebound effect, Somatic hallucination, Somnolence, Substance abuser, Substance dependence, Substance use, Substance use disorder, Substance-induced mood disorder, Substance-induced psychotic disorder, Thinking abnormal, Withdrawal arrhythmia, Withdrawal syndrome)
- increased blood pressure (Blood pressure increased, Blood pressure diastolic increased, Blood pressure systolic increased, Hypertensive crisis, Hypertensive emergency, Hypertension)
- increased heart rate (Heart rate increased, Tachycardia, Extrasystoles)
- transient dizziness/vertigo (Dizziness, Dizziness exertional, Dizziness postural, Procedural Dizziness, Vertigo, Vertigo labyrinthine, Vertigo positional, Vertigo CNS origin);
- impaired cognition (Cognitive disorder);
- cystitis (Allergic cystitis, Chemical cystitis, Cystitis, Cystitis erosive, Cystitis haemorrhagic, Cystitis interstitial, Cystitis noninfective, Cystitis ulcerative, Cystitis-like symptom, Pollakiuria, Dysuria, Micturition urgency, Nocturia);
- anxiety (Anticipatory anxiety, Anxiety, Anxiety disorder, Agitation, Fear, Feeling jittery, Irritability, Nervousness, Panic attack, Tension).

The number and percentage of subjects taking concomitant medication for dissociation events (preferred term of Dissociation) at any time during each induction phase will be provided.

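### SAP 5.1 leaves derealization out of both the dissociation-medication summary and the abuse-potential list, although the CADSS scores it as dissociation; two descriptive rates can be understated by an unknown amount, possibly zero

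*SAP*

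**What the plan says.** Protocol 11.8 leaves the detailed listing of adverse events of special interest to the SAP. SAP 5.1 supplies it as categories, each followed by a bracketed set of preferred terms with no open-ended wording, so the lists are closed.

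- **Abuse potential.** The detachment terms fall in the run "Disorientation, Dissociation, Dissociative disorder, Dizziness, Drug abuse, Drug abuser". The alertness term falls in "Rebound effect, Somatic hallucination, Somnolence, Substance abuser". No derealization or depersonalization term appears in this category or in any other special-interest category.
- **Medication for dissociation.** The SAP will give the number and percentage of subjects "taking concomitant medication for dissociation events (preferred term of Dissociation) at any time during each induction phase". One preferred term defines the event.

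Two other places bear on this.

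- **Japanese Phase 1 experience (Protocol 1.1.2.1, study ESKETINTRD1002).** There, "15 healthy Japanese and 14 healthy Caucasian subjects received single intranasal doses of esketamine 28 mg, 56 mg, and 84 mg" in a crossover. The result is given by preferred term: "The most commonly reported TEAEs by preferred term (>10%) in Japanese subjects were headache", and the list goes on to include "derealization (20.0% [3/15] of subjects". Dissociation is not in that list.
- **CADSS scoring (SAP 5.5.2, Table 8).** Derealization is one of three components of the dissociation scale, with depersonalization and amnesia.

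**The concern.** Perceptual change, described as dissociative symptoms, and potential abuse liability are both secondary safety objectives (Protocol 2.1, SAP 1.1). The scale and the adverse event summaries serve these objectives with different definitions. For the CADSS, derealization is dissociation. For the medication summary and the abuse-potential grouping, it is not.

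A subject whose only relevant event is coded to derealization would be missing from the abuse-potential rate. Medication given for that event would be missing from the dissociation-medication rate. Because derealization was reported after esketamine in Japanese volunteers, any omission would be expected to fall mainly on the active arms. The SAP gives no reason for leaving the term out, while listing Somnolence and Confusional state, each reported in 2 of 15 of the same volunteers.

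**Working it through.** **1. Phase 1 figures reproduced.** Derealization: 3/15 = 20.0%, as stated in Protocol 1.1.2.1. The exact (Clopper-Pearson) 95% interval is 4.3% to 48.1%, so the rate is poorly known.

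**2. How often the term Dissociation was used there.** With 15 subjects, 1/15 = 6.7% and 2/15 = 13.3%. A list of terms above 10% therefore holds every term seen in 2 or more subjects. If the list is complete, Dissociation was reported in at most 1 of 15, against 3 of 15 for derealization.

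**3. Term check against SAP 5.1.** Each Phase 1 term of a perceptual, alertness or balance type was looked up in the special-interest lists.

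| Phase 1 preferred term | Subjects | In SAP 5.1 special-interest lists? |
|---|---|---|
| Vertigo | 7/15 | Yes, dizziness/vertigo |
| Somnolence | 2/15 | Yes, abuse potential |
| Confusional state | 2/15 | Yes, abuse potential |
| Derealization | 3/15 | No |
| Depressed level of consciousness | 2/15 | No |

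**4. Weight of derealization in the SAP's own scale.** Table 8 assigns it items 1, 2, 8 to 13, 16 to 19 and 21: 2 + 6 + 4 + 1 = 13 items. The other components have 7 (depersonalization) and 3 (amnesia), and 13 + 7 + 3 = 23. On the score range, derealization carries 13 × 4 = 52 of 92 points.

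**5. What the omission does to the abuse-potential rate.** Let A be the subjects with at least one listed term, D those with derealization, and n the arm size. The plan reports |A|/n. With derealization added it would be |A ∪ D|/n. The difference is (|D| − |A ∩ D|)/n, which lies between 0 and |D|/n. The documents do not give the overlap. In the Phase 1 study, the four reports of somnolence and confusional state could cover all three derealization subjects or none, so the difference there is anywhere from 0/15 to 3/15 (0 to 20.0 percentage points). That range is too wide to project onto this trial.

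**6. What it does to the medication rate.** The subjects missed are those medicated for derealization and not for an event coded Dissociation. The documents give no count of subjects medicated for either event, so only the lower bound of zero can be stated.

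**7. Whether another table repairs it.** SAP 5.1 tabulates all treatment-emergent events by preferred term, so derealization will be visible. Those rows cannot be added to the grouped rate because subjects overlap. The concomitant therapy table in SAP 3.5 is by generic drug name, not by the event treated, so it does not show medication for derealization.

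**The case against.** The strongest reply is that closer evidence favours the SAP list. Panel B of ESKETINTRD2003 (Protocol 1.1.2.3) studied Japanese patients with treatment-resistant depression, not healthy volunteers. Its double-blind events at 10% or more in any group included somnolence, dizziness, feeling abnormal and dissociation, all on the abuse-potential list, and derealization was not among them. Panel B was small and tested 14 mg and 56 mg, so it says nothing about 28 mg or 84 mg. It is still the nearer population, and it makes a large undercount less likely. This stands.

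Second, the objectives are served elsewhere. The CADSS total and component scores are taken before and after each dose, all events are tabulated by preferred term, and POMS-2 is the protocol's named instrument for abuse liability. No test depends on the special-interest groupings. This also stands and keeps the point minor. It does not supply a grouped rate that includes derealization, or any table of medication given for it.

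Third, few subjects may be medicated for such events. Protocol 1.1.2.3 describes esketamine's adverse events as transient and typically over within 2 hours. The rescue medications in Protocol Section 8 are for agitation or anxiety and for nausea. This is a fair reason to expect a small effect on the medication summary.

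Fourth, the list was chosen deliberately: SAP Amendments 1 and 2 both say it was updated to follow the global Phase 3 trials. Comparability is a good reason to keep that list, but not a reason to show it alone.

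**Conclusion.** The point holds as a small descriptive gap. SAP 5.1 uses a narrower definition of dissociation in two adverse event summaries than the CADSS scoring in SAP 5.5.2, and the term left out was reported in 3 of 15 Japanese Phase 1 subjects. The two rates can be understated. The size cannot be computed and may be zero. The primary endpoint and its test are unaffected.

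Three stronger readings may tempt a reader, and the documents do not support them.

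- **That derealization was the commonest event in Japanese subjects.** Vertigo (7/15, 46.7%), headache and vomiting (4/15, 26.7% each) were more frequent, and nausea was equal at 3/15.
- **That the Phase 1 proportion can be multiplied up to a number missed per arm.** It pools subjects over a three-dose crossover of single doses in healthy volunteers, so it is not a rate for any one dose. It also ignores overlap with listed terms and, for the second summary, whether any medication was given.
- **That depressed level of consciousness is wrongly missing from both summaries.** The protocol reports "depressed level of consciousness (13.3% [2/15] of subjects", and the term is in no special-interest list. It is not a dissociative event, however, so it does not belong in a dissociation-medication summary. Adding it to the abuse-potential grouping, which already contains Somnolence, is optional.

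The conclusion assumes that derealization will be coded to a term not on the list. SAP 5.1 names MedDRA version 20.0 or above, and the protocol does not give the Phase 1 version. If the version in use codes it to a listed term, the abuse-potential gap closes. If it codes it to Dissociation itself, both gaps close.

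**What to change.** Before unblinding, make two changes in SAP 5.1.

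1. For the concomitant-medication summary, define dissociation events as Dissociation, Dissociative disorder, and the preferred term or terms to which the MedDRA version in use codes derealization and depersonalization.
2. Keep the global Phase 3 abuse-potential list unchanged as one row. Add a second row that also includes the derealization and depersonalization term or terms.

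The cost is a wording change and one extra row in a planned table. No new data are collected and no clinical procedure changes. The drawback is a slight departure from the Phase 3 term list, which showing both rows deals with.

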5.2. Clinical Laboratory Tests

Descriptive statistics (N, mean, median, minimum, and maximum) for values and changes from baseline will be provided for clinical laboratory tests (hematology, chemistry and urinalysis) at each scheduled time point for each induction phase (DB and OL).

Clinical laboratory tests that meet the criteria for markedly abnormal will be listed by subject for each induction phase. The incidence of treatment-emergent markedly abnormal (TEMA) laboratory values that occurred at any time during each induction phase will be presented. Clinical laboratory test values will be considered TEMA using the criteria defined by Janssen Research & Development, LLC listed in [Attachment 1](#). The identification of TEMA laboratory values is based on the postbaseline value being out of range while the baseline value is either missing or within the range given in [Attachment 1](#). If postbaseline laboratory results are above the upper limit and the baseline value is below the lower limit, then the postbaseline abnormality will also be considered TEMA. The same applies to the postbaseline value being below the lower limit with the baseline value being above the upper limit.

The incidence of subjects with ALT values $>3 \times$ upper normal limit (ULN) will be presented for each induction phase. Additionally, incidence of hepatic toxicity (Hy's Law)¹² defined as ALT values $>3 \times$ ULN AND total bilirubin values $>2 \times$ ULN will be presented for each induction phase. Similar to the markedly abnormal analysis, only subjects with baseline ALT values $\leq 3 \times$ ULN (AND baseline total bilirubin values $\leq 2 \times$ ULN for hepatic toxicity) (or if baseline value is missing) will be eligible for these analyses.

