The PK/PD relationship of intranasal esketamine and MADRS total score (and possibly selected AEs as additional PD parameters) may be evaluated. If there is any visual trend in graphical analysis, suitable models will be applied to describe the exposure-effect relationships. The results of the PK/PD evaluation will be presented in a separate report.

Safety Analyses

Safety analysis set will consist of all randomized subjects who receive at least 1 dose of intranasal study drug in the double-blind induction phase. Safety data for the double-blind period will be analyzed for this population. For the analysis of safety data in the OL induction phase, all subjects who received at least 1 dose of intranasal study drug in this period will be analyzed.

Adverse events will be coded using the Medical Dictionary for Regulatory Activities (MedDRA). For each AE, the percentage of subjects who experience at least 1 occurrence of the given event will be summarized by treatment group. Subjects who discontinue treatment due to an AE and serious adverse events (SAEs) will be summarized separately.

The TEAEs of special interest will be examined separately grouped in the following categories: Drug abuse, dependence and withdrawal (standardized MedDRA queries [SMQ]), increased blood pressure, increased heart rate, transient dizziness/vertigo, impaired cognition, anxiety, and cystitis. AEs of special interest will be further listed in the SAP.

Body weight, vital signs, 12-lead ECG, pulse oximetry, and clinical laboratory test results, and changes from baseline will be presented over time by treatment group, using descriptive statistics. Any treatment-emergent abnormalities will be presented.

PWC-20 rating scale, dissociative data from the CADSS, alertness data from the CGADR, sedation data from the MOAA/S, suicide-related thoughts and behaviors based on C-SSRS, Abuse-liability data from POMS-2, and psychosislike effect data from the BPRS+ will be summarized descriptively at each scheduled visit by treatment group.

TIME AND EVENTS SCHEDULE 1 [-SCREENING PHASE, PROSPECTIVE LEAD-IN PHASE AND DOUBLE-BLIND INDUCTION PHASE]

	Screening Phase	Prospective Lead-in Phase			Double-blind Induction Phase											
Visit number	1.1 ^b	2.1 ^b	2.2	2.3	3.1 ^a	3.2	3.3	3.4	3.5	3.6	3.7	3.8	3.9	3.10 ^m	EW ^c	
Study Week	Within 4 weeks of Day P1	-6	-4	-2	1		2		3		4			—		

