
 Dipstick -specific gravity -pH -glucose -protein -blood -ketones -bilirubin -urobilinogen -nitrite -leukocyte esterase 	
 Sediment (if dipstick result is abnormal) -red blood cells -white blood cells -epithelial cells -crystals -casts -bacteria
--	--

If dipstick result is abnormal, flow cytometry or microscopy will be used to measure sediment. In case of discordance between the dipstick results and the flow cytometric results, the sediment will be examined microscopically.

The following tests will be done at time points specified in the [TIME AND EVENTS SCHEDULE 1](#), [TIME AND EVENTS SCHEDULE 2](#), and [TIME AND EVENTS SCHEDULE 3](#).

- Lipid panel: total cholesterol, low density lipoprotein (LDL) cholesterol, high density lipoprotein (HDL) cholesterol, and triglycerides
- Serum and urine pregnancy testing (for women of childbearing potential only)
- Urine Drug Screen: barbiturates, methadone, opiates, cocaine, phencyclidine, and amphetamine/methamphetamine
 - The central laboratory will analyze the urine drug screen performed at screening.
- TSH (screening only)
- HbA1c test (screening only)

Electrocardiogram (ECG)

The 12-lead ECG will be collected at time points specified in the [TIME AND EVENTS SCHEDULE 1](#) and [TIME AND EVENTS SCHEDULE 3](#).

During the collection of ECGs, subjects should be in a quiet setting without distractions (eg, television, cell phones). Subjects should rest in a supine position for at least 5 minutes before ECG collection and should refrain from talking or moving arms or legs.

If blood sampling or vital sign measurement is scheduled for the same time point as ECG recording, the procedures should be performed in the following order: ECG(s), vital signs, blood draw.

All ECG tracings will be sent to a central ECG laboratory. The ECGs will be read at the scheduled time points and summarized by a central ECG laboratory. The central ECG laboratory will send the sponsor an electronic copy of the data for inclusion in the clinical database. In addition, the investigator or sub-investigator is required to review all ECGs at the study visit to assess for any potential safety concerns or evidence exclusionary conditions prior to dosing.

Vital Signs (Temperature, Heart Rate, Respiratory Rate, Blood Pressure)

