11.8. Safety Analyses

Safety analysis set will consist of all randomized subjects who receive at least 1 dose of intranasal study drug in the double-blind induction phase. Safety data for the double-blind period will be analyzed for this population. For the analysis of safety data in the OL induction phase, all subjects who received at least 1 dose of intranasal study drug in this period will be analyzed.

Adverse Events

For each AE, the number of subjects who experience at least 1 occurrence of the given event will be summarized by treatment group.

The verbatim terms used in the eCRF by investigators to identify AEs will be coded using the Medical Dictionary for Regulatory Activities (MedDRA). The TEAEs are AEs with onset during the treatment phase or that are a consequence of a preexisting condition that has worsened since baseline. All reported AEs will be included in the analysis. For each AE, the percentage of subjects who experience at least 1 occurrence of the given event will be summarized by treatment group. In addition, comparisons between treatment groups will be provided if appropriate.

The TEAEs of special interest will be examined separately (please refer to Section 3.2.6). The AEs of special interest will be further listed in the SAP.

Summaries, listings, datasets, or subject narratives may be provided, as appropriate, for those subjects who die, who discontinue treatment due to an AE, or who experience a severe or an SAE.

Clinical Laboratory Tests

Laboratory data will be summarized by type of laboratory test. Markedly abnormal results (specified in the SAP) will be used in the summary of laboratory data. Descriptive statistics will be calculated for each laboratory analyte at each respective scheduled time point in each phase of the study. Changes from baseline results will be presented. Frequency tabulations of the abnormalities will be made. A listing of subjects with any markedly abnormal laboratory results will also be provided.

Electrocardiogram (ECG)

The effects on cardiovascular variables will be evaluated by means of descriptive statistics and frequency tabulations. These tables will include observed values and changes from baseline values.

Electrocardiogram data will be summarized by ECG parameter. Descriptive statistics will be calculated at baseline and for observed values and changes from baseline at each scheduled time point. Frequency tabulations of the abnormalities will be made.

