12.1. Definitions

12.1.1. Adverse Event Definitions and Classifications

Adverse Event

An AE is any untoward medical occurrence in a clinical study subject administered a medicinal (investigational or non-investigational) product. An AE does not necessarily have a causal relationship with the treatment. An AE can therefore be any unfavorable and unintended sign (including an abnormal finding), symptom, or disease temporally associated with the use of a medicinal (investigational or non-investigational) product, whether or not related to that medicinal (investigational or non-investigational) product. (Definition per International Conference on Harmonization [ICH])

This includes any occurrence that is new in onset or aggravated in severity or frequency from the baseline condition, or abnormal results of diagnostic procedures, including laboratory test abnormalities.

Note: The sponsor collects AEs starting with the signing of the ICF (refer to Section 12.3.1, All AEs, for time of last AE recording). Exacerbation of primary disease is not defined as AE.

Serious Adverse Event

An SAE based on ICH and EU Guidelines on Pharmacovigilance for Medicinal Products for Human Use is any untoward medical occurrence that at any dose:

- Results in death
- Is life-threatening
(The subject was at risk of death at the time of the event. It does not refer to an event that hypothetically might have caused death if it were more severe.)
- Requires inpatient hospitalization or prolongation of existing hospitalization
- Results in persistent or significant disability/incapacity
- Is a congenital anomaly/birth defect
- Is a suspected transmission of any infectious agent via a medicinal product
- Is Medically Important*

*Medical and scientific judgment should be exercised in deciding whether expedited reporting is also appropriate in other situations, such as important medical events that may not be immediately life-threatening or result in death or hospitalization but may jeopardize the subject or may require intervention to prevent 1 of the other outcomes listed in the definition above. These should usually be considered serious.

If a serious and unexpected AE occurs for which there is evidence suggesting a causal relationship between the study drug and the event (eg, death from anaphylaxis), the event must

be reported as a serious and unexpected suspected adverse reaction even if it is a component of the study endpoint (eg, all-cause mortality).

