| Gamma glutamyl transferase [U/L] | N/A | 300 |
| Glucose [mmol/L] | 2.2 | 16.7 |
| Phosphate [mmol/L] | 0.7 | 2.6 |
| Potassium [mmol/L] | 3.0 | 5.8 |
| Sodium [mmol/L] | 125 | 155 |
| Bilirubin, total [μ mol/L] | N/A | 51.3 |
| Protein, total [g/L] | 50 | N/A |
| Urine pH | N/A | 8.0 |
| Hematocrit [fraction] - female | 0.28 | 0.5 |
| - male | 0.24 | 0.55 |
| Hemoglobin [g/L] | 80 | 190 |
| Neutrophils, segmented [%] | 30 | 90 |
| Monocytes [%] | N/A | 20 |
| Eosinophils [%] | N/A | 10 |
| Basophils [%] | N/A | 6 |
| Lymphocytes [%] | 10 | 60 |
| Platelet count [$\times 10^9$ /L] | 100 | 600 |
| Red blood cell count [$\times 10^{12}$ /L] -- female | 3.0 | 5.5 |
| -- male | 3.0 | 6.4 |
| White blood cell count [$\times 10^9$ /L] | 2.5 | 15.0 |
| Hy's Law criteria: | | |
| Alanine transaminase (SGPT) [U/L] | | > 3X ULN |
| AND | | |
| Bilirubin, total [μ mol/L] | | >2X ULN |

Note: The same limits apply to both males and females unless sex is indicated; N/A = Not applicable.

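### SAP 5.2 and Attachment 1 set an abnormality limit for urine pH only, so 15 of the 16 urinalysis items collected get no abnormality count or listing

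*SAP*

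**What the plan says.** **Protocol.** Section 11.8, under clinical laboratory tests, states: "Frequency tabulations of the abnormalities will be made. A listing of subjects with any markedly abnormal laboratory results" is also planned. The same paragraph leaves the markedly abnormal criteria to the SAP. The synopsis, speaking of weight, vital signs, ECG, oximetry and laboratory results together, adds: "Any treatment-emergent abnormalities will be presented". Section 9.6 lists 10 urine dipstick items and 6 sediment items. The sediment is conditional: "Sediment (if dipstick result is abnormal").

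**SAP.** Section 5.2 names urinalysis once, in the descriptive statistics: "values and changes from baseline will be provided for clinical laboratory tests (hematology, chemistry and urinalysis"). The statistics are N, mean, median, minimum and maximum; no standard deviation is listed. Incidence comes through the treatment-emergent markedly abnormal (TEMA) rule: "Clinical laboratory test values will be considered TEMA using the criteria defined by" the sponsor, as listed in Attachment 1. The by-subject listing is likewise restricted to tests that meet the markedly abnormal criteria. The separate ALT and Hy's Law incidences do not concern urine. The only urine row in Attachment 1 is "Urine pH | N/A | 8.0". SAP Table 1 gives laboratory visit windows for hematology and chemistry and names no window for urinalysis.

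**The concern.** Dipstick blood, leukocyte esterase, nitrite and protein are normally reported as negative or as a grade. The useful safety summary for such results is how many subjects per arm became abnormal who were not so at baseline. The SAP does this for blood chemistry and hematology (TEMA), vital signs (Table 5) and ECG (Table 6). It does not do it for urine, apart from pH.

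The gap has some relevance to this drug. Protocol 1.1.2.3 describes ketamine-related ulcerative cystitis, with blood in the urine and urge incontinence among its symptoms, and cystitis is an adverse event category of special interest in SAP 5.1. The dipstick is a scheduled measurement in every arm. What is at stake is one descriptive safety comparison by dose against placebo.

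**Working it through.** The plan states no figure to reproduce. The check is a count, followed by a small example of what the planned statistics can show.

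**Count of items (Protocol 9.6 against SAP Attachment 1)**
- Dipstick: specific gravity, pH, glucose, protein, blood, ketones, bilirubin, urobilinogen, nitrite, leukocyte esterase = 10.
- Sediment: red cells, white cells, epithelial cells, crystals, casts, bacteria = 6.
- Collected: 10 + 6 = 16. With a limit in Attachment 1: pH only = 1. Without: 16 − 1 = 15.
- Attachment 1 also has rows for glucose (mmol/L), total protein (g/L), total bilirubin (μmol/L) and red and white cell counts. Their units are those of blood tests, so they do not serve the urine items.

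**Can the planned statistics stand in for a count at one visit?** Inputs: 37 subjects per esketamine arm (Protocol 11.2). Assumed: 0/1 coding and 4 subjects positive at baseline; the documents give neither.
- Arm A: 3 persist, 1 resolves, 1 is new. Arm B: 4 resolve, 4 others are new.
- Values in both arms, at baseline and at the visit: mean 4/37 = 0.108, median 0, minimum 0, maximum 1.
- Changes in both arms: mean (1 − 1)/37 = 0 in A and (4 − 4)/37 = 0 in B; median 0, minimum −1, maximum +1.
- New positives: 1/37 = 2.7% in A and 4/37 = 10.8% in B. Every planned statistic is the same.

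**Graded coding 0 to 3 (assumed), all negative at baseline.** Positive grades {3, 3}, {3, 2, 1} and {3, 1, 1, 1} each sum to 6. All three give mean 6/37 = 0.162, median 0, minimum 0 and maximum 3, for 2 (5.4%), 3 (8.1%) or 4 (10.8%) subjects.

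**Over the phase.** The schedule has two postbaseline urinalyses in the double-blind phase, one mid-phase and one on Day 28. Two new positives at each could be the same 2 subjects (2/37 = 5.4%) or 4 different ones (4/37 = 10.8%). Summaries by visit cannot tell these apart.

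**Where the planned statistics do suffice.** A maximum change of 0 with N = 37 means that nobody worsened at that visit. The one-sided 95% upper bound on the rate is then 1 − 0.05^(1/37) = 7.8%.

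**Sediment.** It is examined only after an abnormal dipstick, so its mean describes a selected subset, not the arm.

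**The case against.** The strongest reply is that the protocol is honoured. Section 11.8 speaks of laboratory data in general and hands the markedly abnormal criteria to the SAP. SAP 5.2 then tabulates the incidence of abnormalities so defined and lists them. On that reading, the only question is which analytes deserve a limit, and the sponsor applied its standard list. This stands in part: the SAP does have a frequency method, and what is missing is urine criteria to feed it. Delegating the criteria still does not explain why a panel of 16 items has one limit, or why graded results get means.

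A reader might infer that Protocol 11.8 promises tables for particular urine parameters relevant to cystitis. It does not. It names no urine item and no cystitis purpose, and any priority subset is a reviewing judgement.

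The second reply is that cystitis is covered elsewhere, and this carries weight. The adverse event definition takes in "or abnormal results of diagnostic procedures, including laboratory test abnormalities". Protocol 9.6 requires the investigator to review each laboratory report and record clinically relevant changes as adverse events. SAP 5.1 counts events by preferred term, including a 13-term cystitis category. Haematuria and urge incontinence are not among the 13, but would appear under their own terms if reported. What is lost is mainly positives that the investigator judged not relevant. Protocol 1.1.2.3 also places most ketamine cystitis cases in near-daily recreational users, whereas a course here is eight supervised doses.

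Third, the numerical example is built so that the statistics coincide, and it uses all 37 subjects although 12.5% drop-out is planned (37 × 0.875 = 32.4). That is fair. It shows that the planned statistics can hide the count, not that they will.

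**Conclusion.** The point holds as a gap in criteria and an ill-suited summary. Of 16 urinalysis items, 15 have no abnormality criterion and therefore no incidence table or listing, and categorical results are summarised as if they were continuous. The count of 15 rests on the text alone. The example (2.7% against 10.8% behind identical statistics) rests on assumed coding and an assumed baseline rate. That dipstick results are categorical is also an assumption, because the documents do not state the reporting scale.

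Three stronger readings are not supported: that the SAP plans no frequency table of laboratory abnormalities (it plans TEMA incidence), that it breaks a promise specific to urine or cystitis, and that a cystitis signal would go unseen (the adverse event route remains). The change is optional, and no efficacy result depends on it.

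**What to change.** In SAP 5.2, for the categorical dipstick items (blood, leukocyte esterase, nitrite and protein first) and for sediment red and white cells, replace mean and median by:

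- a shift table from baseline to worst postbaseline category, in the format that SAP 5.5.1 already uses for the C-SSRS;
- treatment-emergent incidence by treatment group in each induction phase, reusing the TEMA logic ("the postbaseline value being out of range while the baseline value is either missing or within the range") with the central laboratory's normal category as the limit.

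Use all subjects with a postbaseline dipstick as the denominator, and count a negative dipstick as no sediment abnormality. Keep descriptive statistics for pH and specific gravity, and leave the cystitis adverse event list unchanged.

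This covers 8 dipstick items (10 less pH and specific gravity) and 2 sediment items. The other 5 of the 15 (specific gravity and 4 sediment items) stay as planned, by choice of priority.

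The cost is SAP wording and two tables from data already collected, with no new sample or visit. The normal category has to be written down, since the documents do not define it. Some positives will be minor, menstrual or infectious. The placebo arm gives that background rate in the double-blind phase only; the open-label phase has no control.
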